## **Appendix 1a**

### **Schedule of Activities: Randomized Treatment Phase (Treatment Period) (cont.)**

- s If serum sickness or a clinically significant allergic drug reaction is suspected, the Sponsor should be notified, and serum for etrolizumab level and ADAs should be drawn and sent to the central laboratory. ADA samples may also be utilized for exploratory PD assessments or assessment of drug concentrations.
- t A blood sample to test for antibodies to JCV will be taken and stored for possible later assessment of how widespread the JCV infection is in the study population. Sample testing for the presence of JCV antibodies is not helpful in predicting risk for PML or for evaluating neurologic symptoms. The sample may be tested if there is a strong belief that this information will be helpful in managing a patient's condition.
- u PUCAI and PCDAI should be calculated prior to randomization. For children who are 6 years of age or younger, the parent or caregiver can respond to the questions on the patient's behalf.
- v IF REQUIRED: Only if there is suspicion for clinically significant CMV colitis, one biopsy sample should be obtained from the base of the ulcer to evaluate for histological presence of CMV. Analysis should be performed locally if possible, or can be sent to a central laboratory if necessary. Result must be negative for CMV prior to dosing on Day 0.
- w Randomization to occur prior to first dose at Day 0.
- x Patients will be randomized in a 1:1 ratio to receive either high-frequency dose of etrolizumab once every 4 weeks or low-frequency dose of etrolizumab once every 8 weeks. The high-frequency dose of 1.5 mg/kg etrolizumab will be administered once every 4 weeks at Weeks 0, 4, 8, and 12. The low-frequency dose of 3 mg/kg etrolizumab will be administered once every 8 weeks at Weeks 0 and 8.

**Appendix 1b**  
**Schedule of Assessments: Randomized Treatment Phase (Safety Follow-up Period)**

Assessments	Week ( $\pm 3$ days)			Unscheduled Visit b
	Week 18	Week 20	Week 24 or Early Withdrawal Visit a	
Concomitant medications	x	x	x	x
Adverse events	x	x	x	x
ECG			x	
Urine pregnancy test c			x	
Physical examination		x	x	x
PD (receptor occupancy), flow cytometry sampling (whole blood) d	x	x	x	
Serum PD measures (MAdCAM-1) d	x	x	x	
PK sampling (serum) d	x	x	x	
Anti-drug antibody sample (serum) e, f			x	
PML neurologic examination g		x	x	x

## **Appendix 1b**

### **Schedule of Assessments: Randomized Treatment Phase (Safety Follow-up Period) (cont.)**

---

ADA=anti-drug antibody; ECG=electrocardiogram; MAdCAM-1=mucosal vascular addressin cell adhesion molecule-1; PD=pharmacodynamic; PK=pharmacokinetic; PML=progressive multifocal leukoencephalopathy.

- a All assessments indicated for the Early Withdrawal Visit should be performed if the patient discontinues prior to completion of the 8-week safety follow-up period.
- b Unscheduled visit for safety monitoring.
- c A urine test may be performed; however, if urine test result is positive, a confirmatory serum test must be performed. A urine pregnancy test is only required in female patients at Tanner Stage 2 or greater, or after onset of menarche. The test must be performed on a fresh voided sample.
- d PD and PK samples will be collected at Days 126 (Week 18), 140 (Week 20) and 168 (Week 24).
- e If serum sickness or a clinically significant allergic drug reaction is suspected, the Sponsor should be notified and serum for *the analysis of study drug level* and ADAs should be drawn and sent to the central laboratory. ADA samples may be used for PK and/or exploratory PD assessments.
- f ADA samples only need to be taken on Week 24 and at the Early Withdrawal Visit.
- g PML neurologic examination consists of the PML Subjective Checklist. Administer before other assessments as per [Appendix 7](#).

**Appendix 1c**  
**Schedule of Assessments: Open-Label Extension Phase**

**Clinic Visits Week 0–Week 44**

Assessments	Etrolizumab Administration Every 4 Weeks											
	Clinic Visit Starting at Day 1 of Week 0 ( $\pm$ 3 days)											
	0 a,b	4	8	12	16	20	24	28	32	36	40	44
Vital signs (BP, pulse rate)	x			x			x			x		
ECG	x											
Concomitant medications	x	x	x	x	x	x	x	x	x	x	x	x
Height	x	x	x	x			x			x		
Weight	x	x	x	x	x	x	x	x	x	x	x	x
Tanner Stage	x											
Adverse events	x	x	x	x	x	x	x	x	x	x	x	x
Limited symptom driven physical examination, including GI	x	x		x			x			x		
PML neurologic examination e	x			x			x			x		
PUCAI and PCDAI f		x	x	x			x			x		
Pregnancy test g	x	x	x	x	x	x	x	x	x	x	x	x
Hematology	x	x h	x h	x			x			x		
ESR h		x	x	x			x			x		

**Appendix 1c**  
**Schedule of Assessments: Open-Label Extension Phase (cont.)**

**Clinic Visits Week 0–Week 44 (cont.)**

Assessments	Etrolizumab Administration Every 4 Weeks											
	Clinic Visit Starting at Day 1 of Week 0 ( $\pm$ 3 days)											
	0 a,b	4	8	12	16	20	24	28	32	36	40	44
Chemistry	x	x h	x h	x			x			x		
Hepatitis B DNA i	x			x			x			x		
Serum sample (CRP)	x											
Etrolizumab PK sample (serum) j	x			x								
Anti-drug antibody sample (serum) j, k	x			x								
Etrolizumab administration	x	x	x	x	x	x	x	x	x	x	x	

**Appendix 1c**  
**Schedule of Assessments: Open-Label Extension Phase (cont.)**

**Clinic Visits Week 48-Week 92**

Assessments	Etrolizumab Administration Every 4 Weeks											
	Clinic Visit (± 7 days)	Clinic Visit (± 3 days)										
		48	52	56	60	64	68	72	76	80	84	88
Vital signs (BP, pulse rate)	x			x			x			x		
ECG	x											
Concomitant medications	x	x	x	x	x	x	x	x	x	x	x	x
Height	x			x			x			x		
Weight	x	x	x	x	x	x	x	x	x	x	x	x
Tanner Stage												
Adverse events	x	x	x	x	x	x	x	x	x	x	x	x
Limited symptom driven physical examination, including GI		x		x			x			x		
PML neurologic examination e	x			x			x			x		
PUCAI and PCDAI f	x			x			x			x		
Pregnancy test g	x	x	x	x	x	x	x	x	x	x	x	x
Hematology	x			x			x			x		

**Appendix 1c**  
**Schedule of Assessments: Open-Label Extension Phase (cont.)**

**Clinic Visits Week 48-Week 92 (cont.)**

Assessments	Etrolizumab Administration Every 4 Weeks											
	Clinic Visit ( $\pm$ 7 days)	Clinic Visit ( $\pm$ 3 days)										
		48	52	56	60	64	68	72	76	80	84	88
ESR h	x			x			x			x		
Chemistry	x			x			x			x		
Hepatitis B DNA i	x			x			x			x		
Serum sample (CRP)	x											
Etrolizumab PK sample (serum) j	x											
Anti-drug antibody sample (serum) j, k	x											
Etrolizumab administration	x	x	x	x	x	x	x	x	x	x	x	x

**Appendix 1c**  
**Schedule of Assessments: Open-Label Extension Phase (cont.)**

**Clinic Visits Week 96–Week 312, Unscheduled, and Early Withdrawal from Treatment**

Assessments	Clinic Visit (± 7 days)	Clinic Visit (± 3 days)	Clinic Visit (± 3 days)	Clinic Visit (-14 days)	Unscheduled Visit c	Early Withdrawal from Treatment Visit d
	Weeks 96, 120, 144, 168, 192, 216, 240, 264, 288	Weeks 100, 104 , 112, 116, 124, 128, 136, 140, 148, 152, 160, 164, 172, 176, 184, 188, 196, 200, 208, 212, 220, 224, 232, 236, 244, 248, 256, 260, 268, 272, 280, 284, 292, 296, 304, 308	Weeks 108, 132, 156, 180, 204, 228, 252, 276, 300	Week 312		
Vital signs (BP, pulse rate)	x		x	x		x
ECG	x		x			x
Concomitant medications	x	x	x	x	x	x
Height	x		x	x	x	x
Weight	x	x	x	x	x	x
Tanner Stage	x		x	x	x	x
Adverse events	x	x	x	x	x	x
Limited symptom driven physical examination, including GI	x		x	x	x	x
PML neurologic examination e	x		x	x	x c	x
PUCAI and PCDAI f	x		x	x	x c	x

**Appendix 1c**  
**Schedule of Assessments: Open-Label Extension Phase (cont.)**

**Clinic Visits Week 96–Week 312, Unscheduled, and Early Withdrawal from Treatment (cont.)**

Assessments	Clinic Visit (± 7 days)	Clinic Visit (± 3 days)	Clinic Visit (± 3 days)	Clinic Visit (-14 days)	Unscheduled Visit c	Early Withdrawal from Treatment Visit d
	Weeks 96, 120, 144, 168, 192, 216, 240, 264, 288	Weeks 100, 104 , 112, 116, 124, 128, 136, 140, 148, 152, 160, 164, 172, 176, 184, 188, 196, 200, 208, 212, 220, 224, 232, 236, 244, 248, 256, 260, 268, 272, 280, 284, 292, 296, 304, 308	Weeks 108, 132, 156, 180, 204, 228, 252, 276, 300	Week 312		
Pregnancy test g	x	x	x	x	x	x
Hematology	x			x	x	x m
ESR h	x			x	x	x
Chemistry	x			x	x	x m
Hepatitis B DNA i	x			x	x	
Serum sample (CRP)	x				x c	x m
Etrolizumab PK sample (serum) j	x			x	x	
Anti-drug antibody sample (serum) j, k	x			x	x	x l, m
Etrolizumab administration	x	x	x	x	x	

## Appendix 1c

### Schedule of Assessments: Open-Label Extension Phase (cont.)

ADA=anti-drug antibody; BP=blood pressure; CRP=c-reactive protein; ECG=electrocardiogram; eCRF=electronic case report form; ESR=erythrocyte sedimentation rate; GI=gastrointestinal; PD=pharmacodynamics; PK=pharmacokinetic; PCDAI=Pediatric Crohn's Disease Activity Index; PML=progressive multifocal leukoencephalopathy; PUCAI=Pediatric Ulcerative Colitis Activity Index.

- a Day 1 of Week 0.
- b Week 0 procedures and laboratory assessments that have been collected as part of the final visit for the safety follow-up period (within the treatment phase) do not need to be repeated, with the exception of ADAs, which must be recollected at Week 1 if the Week 0 visit occurs > 7 days after the final visit of the safety follow-up period.
- c Unscheduled visit represents a visit that is not as per the Schedule of Assessments and is required for an adverse event or for potential relapse assessment. All indicated assessments are NOT performed at each unscheduled visit. Assessments would be symptom driven (e.g., only perform PML neurologic examination if patient reports symptoms suspected to indicate PML). Assessments corresponding to items noted in this column should be recorded on the eCRF.
- d Denotes the early withdrawal from treatment visit for the open-label treatment period. To be performed within 30 days of last dose of study drug. Study drug is not administered at the Early Withdrawal from Treatment visit.
- e PML neurologic examination consists of the PML Subjective Checklist. Administer before other assessments, per [Appendix 7](#).
- f For children who are 6 years of age or younger, the parent or caregiver can respond to the questions on the patients behalf.
- g A urine test may be performed; however, if the urine test result is positive, a confirmatory serum test must be performed. Do not administer etrolizumab unless the serum pregnancy test result is negative. A urine pregnancy test is only required in female patients at Tanner Stage 2 or greater, or after onset of menarche. Test must be performed on fresh voided sample.
- h For patients with Crohn's disease only. Hematocrit, albumin, and erythrocyte sedimentation rate (ESR) will be collected to calculate the PCDAI score.
- i Assessment is required if the patient becomes Hepatitis B antibody positive. Not mandatory for all patients.
- j All samples to be collected prior to administration of etrolizumab.
- k If serum sickness or a clinically significant allergic drug reaction is suspected, Sponsor should be notified, and serum for etrolizumab level and ADAs should be drawn and sent to the central laboratory. ADA samples may also be utilized for exploratory PD assessments or assessment of drug concentrations.
- l PD and drug concentrations may be assessed from these ADA samples.
- m Not required if unscheduled visit leads to withdrawal and assessment previously conducted at unscheduled visit

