### **3. STUDY DESIGN**

#### **3.1 DESCRIPTION OF THE STUDY**

This pediatric PK/PD study consists of multiple phases. The randomized treatment phase is an open-label, randomized phase in which etrolizumab is administered to patients on the basis of body weight (mg/kg); randomization will be stratified by weight (<40 kg, ≥40 kg). Patients will be randomized in a 1:1 ratio to receive either high-frequency etrolizumab once every 4 weeks (Q4W) or low-frequency etrolizumab once every 8 weeks (Q8W). The high-frequency dose of 1.5 mg/kg etrolizumab will be administered Q4W (Weeks 0, 4, 8, and 12). The low-frequency dose of 3.0 mg/kg etrolizumab will be administered Q8W (Weeks 0 and 8).

After the 24-week randomized treatment phase (which includes a 16-week treatment period and an 8-week safety follow-up period), patients will then have the option to participate in the 312-week OLE phase (treatment with etrolizumab 1.5 mg/kg will be administered Q4W). All patients who participate in the 24-week randomized treatment phase and the 312-week OLE phase *will enter the 12-week safety follow-up period (see Appendix 1d; no etrolizumab treatment) and will complete the safety surveillance PML-monitoring phase (see Appendix 1e; no etrolizumab treatment for a total of 104 weeks)*. All patients who choose not to enter the OLE phase after the 24-week randomized treatment phase will enter the 104-week PML monitoring phase.

Patients can enter the OLE phase after completion of the 24-week randomized treatment phase. If the last visit of the randomized treatment phase and Day 1 of the OLE phase occur on the same day, the assessments from the randomized treatment phase should be completed. The assessments from the randomized treatment phase can apply to the OLE assessments (i.e., the same assessments should not be repeated for the OLE).

The 104-week PML monitoring phase will consist of telephone calls approximately every 6 months (see [Appendix 7](#)) with administration of the PML Subjective Checklist. If there are any signs or symptoms suggestive of PML identified on this subjective checklist during the telephone call, the patient will be asked to come into the clinic for a neurologic examination. The PML Algorithm (see [Appendix 8](#)) will be followed for any suspected

case of PML, and any confirmed case of PML will be reported as a serious adverse event (see Section 5.4.2).

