#### **4.1.1 Inclusion Criteria**

Patients must meet the following criteria for study entry:

- Signed Informed Consent Form by parent or legal guardian
- Age of 4 years to  $<18$  years at the time of signing the Informed Consent Form
- Ability to comply with the study protocol, in the investigator's judgment
- Weight of 13 kg or more

- Diagnosis of UC or CD confirmed by biopsy and established for  $\geq 3$  months (i.e., after first diagnosis by a physician according to American College of Gastroenterology [ACG] guidelines) prior to screening
- Inadequate response, loss of response or intolerance to prior immunosuppressants and/or corticosteroid treatment and/or anti-TNF therapy
- For patients with UC: moderately to severely active UC as determined by an MCS of 6–12 with an endoscopic subscore  $\geq 2$  (within the last 12 months prior to screening) and a rectal bleeding subscore  $\geq 1$
- For patients with CD: moderately to severely active CD as determined by a Pediatric Crohn's Disease Activity Index (PCDAI) score of  $> 30$  at baseline
- Must meet the following surveillance colonoscopy requirements:
  - Document evidence of surveillance for dysplasia every 1 to 2 years, beginning approximately 7 to 10 years after their initial diagnosis
- For postpubertal females of childbearing potential: agreement to remain abstinent (refrain from heterosexual intercourse) or use acceptable contraceptive methods during the treatment period and for at least 24 weeks after the last dose of etrolizumab.

A female is considered to be of childbearing potential if she is postmenarcheal, has not reached a postmenopausal state ( $\geq 12$  continuous months of amenorrhea with no identified cause other than menopause), and has not undergone surgical sterilization (removal of ovaries and/or uterus).

Examples of acceptable contraceptive methods include bilateral tubal ligation, male sterilization, combined oral contraceptive pill or transdermal patch, spermicide and barrier [condoms], intrauterine device, implants for contraception, injections for contraception [with prolonged release], hormonal vaginal device (see [Appendix 6](#)).

The reliability of sexual abstinence should be evaluated in relation to the duration of the clinical trial and the preferred and usual lifestyle of the patient. Periodic abstinence (e.g., calendar, ovulation, symptothermal, or postovulation methods) and withdrawal are not acceptable methods of contraception.

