- John Cunningham virus (JCV) antibodies: A blood sample to test for antibodies to JCV will be taken and stored for possible later assessment of how widespread the JCV infection is in the study population. Sample testing for the presence of JCV antibodies is not helpful in predicting risk for PML or for evaluating neurologic symptoms. The sample may be tested if there is a strong belief that this information will be helpful in managing a patient's condition.
- CRP
- *C. difficile* toxin assay in stool, stool culture and sensitivity testing, stool ova and parasites analysis
- Pregnancy test: All postpubertal female patients (including those who have had a tubal ligation) will have a serum pregnancy test at screening. Urine pregnancy tests will be performed at specified subsequent visits. If a urine pregnancy test result is positive, it must be confirmed by a serum pregnancy test.

- Viral serology and detection tests
  - HBV (HBsAg, total HB core antibody [anti-HBc] and HBV DNA)
  - HCV antibody
  - HCV RNA: Measurement of HCV RNA with use of the Amplicor assay is required when the patient has a known history of HCV antibody positivity with past documentation of undetectable HCV RNA, either with or without history of anti-viral treatment. Patients with newly diagnosed HCV antibody positivity are not eligible for this study and, therefore, do not require measurement of HCV RNA.
  - HIV
- PK assays
  - Serum samples will be collected for determination of etrolizumab concentrations in all patients. Samples will be analyzed using a validated assay.
- Fecal calprotectin testing
- PD biomarker assays
  - Serum samples will be collected and qualified methods will be used to measure MAdCAM-1
  - Serum samples, whole blood, and stool may be assessed for additional exploratory biomarkers
  - Whole blood will be used for flow cytometry with qualified methods to measure  $\beta$ -7 receptor occupancy
- Anti-drug antibody (ADA) assays
  - Serum samples will be collected for detection and characterization of antibodies against etrolizumab in all patients. Samples will be analyzed using a validated assay. For ADA samples without matched PK determinations, etrolizumab concentrations may be measured for the purpose of helping interpret ADA data. ADA samples may also be utilized for exploratory PD biomarkers.

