## **Appendix 6**

### **Childbearing Potential, Pregnancy Testing, and Contraception**

All females of childbearing potential (including those who have had a tubal ligation) will have a serum pregnancy test at screening and a urine pregnancy test prior to administration of study drug at subsequent visits. If a urine pregnancy test result is positive, study drug will not be administered until pregnancy is ruled out. The result must be confirmed by a serum pregnancy test (conducted by the central laboratory). See Section 5.4.3 of the protocol for management of a patient with a confirmed pregnancy.

All postpubertal female patients are considered to be of childbearing potential unless they meet one of the following criteria:

- The patient has been postmenopausal (non-therapy-induced amenorrhea) for at least 12 months
- The patient had a surgical bilateral oophorectomy (with or without hysterectomy) more than 6 weeks prior to enrollment
- The patient had a hysterectomy

Female patients of reproductive or childbearing potential who are unwilling to use a highly effective method of contraception or remain abstinent during the treatment period and for at least 24 weeks after the last dose of study drug will be excluded from study participation.

Abstinence is acceptable only if it is in line with the preferred and usual lifestyle of the patient. Periodic abstinence (e.g., calendar, ovulation, symptothermal, or postovulation methods) and withdrawal are not acceptable methods of contraception.

Examples of highly effective contraception include the following:

- Combined oral contraceptive pill
- Contraceptive transdermal patch
- Intrauterine device
- Implants for contraception
- Injections for contraception (with prolonged release)
- Hormonal vaginal device
- Sterilization, surgical tubal ligation
- Sole sexual partner consisting of surgically sterilized male partner with appropriate postsurgical verification of the absence of spermatozoa in the ejaculate

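### Appendix 1c footnote b lets a site skip the pregnancy test before the first open-label extension dose after any gap, in conflict with Appendix 6 and Section 3.1; its ADA recollection time, Week 1, is probably a slip

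*Combined protocol and SAP*

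**What the plan says.** Appendix 1c lists a pregnancy test at OLE Week 0 and attaches footnotes a and b to that column. Footnote b says that Week 0 procedures and laboratory tests collected at the last safety follow-up visit "do not need to be repeated, with the exception of ADAs, which must be recollected at Week 1". The ADA exception applies when Week 0 falls more than 7 days after that visit. Appendix 1b shows that the visit in question, Week 24, includes a urine pregnancy test.

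Two other places bear on the same visit. Appendix 6 requires, for females of childbearing potential, a serum test at screening and "a urine pregnancy test prior to administration of study drug at subsequent visits". Section 3.1 introduces the reuse of assessments with the condition "If the last visit of the randomized treatment phase and Day 1 of the OLE phase occur on the same day".

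For ADA samples, footnote j of Appendix 1c, attached to the PK and ADA rows, states: "All samples to be collected prior to administration of etrolizumab". The OLE grid is headed "Clinic Visit Starting at Day 1 of Week 0" and continues at Weeks 4, 8, 12 and so on to Week 312.

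**The concern.** The sentence in footnote b provides for a late start and still restores only the ADA sample. It therefore cannot be read as a same-day rule. Everything else collected at Week 24, including the pregnancy test, stays waived after a gap of any length. A site working from the schedule could give the first OLE dose on a result weeks old, while a site working from Appendix 6 would test again. At stake is a pre-dose safety check in adolescents, at the visit where drug is restarted after a long break.

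The second matter is smaller. Footnote b sends the repeat ADA sample to a week at which no OLE visit exists and which comes after the first OLE dose. ADA incidence is an OLE safety endpoint in Table 2, so the instruction should be one that sites can follow.

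**Working it through.** The plan gives no figure to reproduce. The check sets the texts side by side and adds calendar arithmetic on nominal visit days.

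**1. Is the pregnancy test inside the waiver?** Appendix 1b schedules it at Week 24, and footnote b waives Week 0 items collected at that visit. Yes.

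**2. Does anything limit the gap?** Footnote b's 7-day limit belongs to ADAs only. Section 3.1 says that patients can enter the OLE once they have completed the 24-week phase, and sets no latest date. Under footnote b, then:

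- Age of the test at the first OLE dose = gap between Week 24 and OLE Day 1.
- Same-day entry: 0 days, and no conflict.
- Later entry: no stated upper limit. The documents give no expected gap. For assumed gaps of 14, 28 or 56 days, the result is 14, 28 or 56 days old.

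**3. How does this compare with the rest of the schedule?** Scheduled OLE visits, from the columns of Appendix 1c: 12 (Weeks 0–44) + 12 (Weeks 48–92) + 9 + 36 + 9 + 1 (Weeks 96–312) = 79, which equals 312/4 + 1. Every column lists a pregnancy test, and only Week 0 can be waived under footnote b. In the randomized phase the protocol takes the stricter line: screening may be up to 35 days before Day 1, yet Appendix 1a repeats the test on Day 1 before dosing.

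**4. How long has the patient been off drug at Week 24?** The last doses are at Week 12 (Q4W) and Week 8 (Q8W), from Section 3.1.

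- Q4W: 24 − 12 = 12 weeks.
- Q8W: 24 − 8 = 16 weeks.

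**5. How far does the contraception requirement reach?** Section 4.1.1 requires abstinence or contraception "during the treatment period and for at least 24 weeks after the last dose of etrolizumab".

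- Q4W: 12 + 24 = Week 36, so it covers gaps of up to 36 − 24 = 12 weeks after Week 24.
- Q8W: 8 + 24 = Week 32, so it covers gaps of up to 32 − 24 = 8 weeks.

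**6. Can the ADA instruction be followed?** All 79 visits fall at multiples of 4 weeks, so Week 1 is not on the grid. The first OLE dose is at Week 0. A Week 1 sample would come about 7 days after it and cannot serve as a sample before re-exposure.

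**The case against.** The strongest reply is that footnote b is permissive and Appendix 6 is the specific rule. A site can satisfy both by testing at Week 0, where the schedule already marks a test. That is correct: the protocol as a whole still calls for the test, and a reader who inferred that the test has been abolished at Week 0 would go too far. What stands is that two instructions disagree and the one in the schedule is the laxer.

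The second reply is that contraception already protects these patients. It does for each gap illustrated above: 56 days is 8 weeks, the limit for Q8W. Section 5.4.3.1 also requires patients to report pregnancy. The group is small too: postpubertal girls who enter the OLE late, in a study of about 24 patients. These facts limit the risk. They do not make the test redundant, since the protocol requires contraception and still lists a test at every scheduled OLE visit.

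A reader might also cite footnote g, "Test must be performed on fresh voided sample", as a direct contradiction of the waiver. It is not one. It concerns the urine specimen, and the Week 24 test carries the same requirement. Footnote g sets no maximum age for a result, so it neither proves the conflict nor resolves it.

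On ADA, Week 1 is most plausibly a slip for Day 1 of Week 0, which is how footnote a defines the visit. The conflict with footnote j is arguable, since a Week 1 sample still precedes the Week 4 dose. Because ADA is the exception to the waiver, the Week 0 sample may also still be due. A reader might infer that a sample taken a week after dosing would hide antibodies or spoil the OLE immunogenicity results. The documents do not support that: they give no drug tolerance for the assay, the Week 24 ADA sample exists, and Section 6.7 defines no separate OLE baseline. Section 4.5.6 also provides for the missing concentration: "For ADA samples without matched PK determinations, etrolizumab concentrations may be measured for the purpose of helping interpret ADA data".

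**Conclusion.** The pregnancy-test conflict holds and should be corrected. Followed as written, footnote b permits the first OLE dose on a Week 24 result of any age, against Appendix 6 and beyond the same-day carry-over in Section 3.1. It affects one scheduled visit in 79, the one that restarts drug at least 12 weeks (Q4W) or 16 weeks (Q8W) after the last dose. Contraception reduces the risk for gaps of up to 12 or 8 weeks after Week 24, and nothing in the documents limits entry to those gaps.

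This rests on the text and nominal visit days. The documents do not say how long gaps are, how many patients enter late, or how many have yet to enter the OLE. They do not show that any patient was dosed without a current test, and no such claim is made here.

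The ADA timing is a secondary, probably clerical, error with limited effect on the ADA analysis. The primary PK and PD endpoints are untouched.

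**What to change.** In footnote b, state that the pregnancy test must be done before dosing at OLE Week 0 unless it was done the same day, in line with Appendix 6. In the same footnote, change the ADA recollection time from Week 1 to Week 0, pre-dose, keeping the trigger of more than 7 days.

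The cost is one edited footnote, one urine test where applicable, and an ADA sample that footnote b already asks for, all at a visit that already takes place. If every patient has already entered the OLE, the sponsor should instead check delayed entries for a missing Week 0 pregnancy test.

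### Appendix 1c marks an etrolizumab dose at unscheduled open-label extension visits, with no dosing condition, against the four-weekly regimen in Section 3.1

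*Combined protocol and SAP*

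**What the plan says.** Section 3.1 gives the extension regimen in one phrase: "treatment with etrolizumab 1.5 mg/kg will be administered Q4W". The first part of the Appendix 1c schedule repeats the interval in its header, "Etrolizumab Administration Every 4 Weeks".

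The last part of Appendix 1c has six columns: three groups of scheduled weeks, Week 312, Unscheduled Visit, and Early Withdrawal from Treatment. Its dosing row reads "Etrolizumab administration x x x x x", so five of the six cells are marked. The fifth is Unscheduled Visit and the empty one is Early Withdrawal.

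Two footnotes govern these columns:
- **Footnote c** describes the unscheduled visit as one outside the schedule that "is required for an adverse event or for potential relapse assessment". It adds that not every marked assessment is carried out and that the choice depends on symptoms. It does not mention drug administration.
- **Footnote d** states that no study drug is given at the Early Withdrawal visit. It makes no such statement for the unscheduled visit.

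Three other places bear on the same question:
- **Appendix 1a** has an unscheduled column for the randomized phase, with no dosing mark for either regimen.
- **Section 5.1.1.1.1 and Table 4** suspend drug when PML is suspected. Table 4 also withholds it during a serious infection.
- **Section 4.3.2.1** ties each injection to a treatment visit under the patient's regimen.

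**The concern.** A site works from the schedule table. Here the table marks drug at a visit that exists because something has gone wrong between doses, and nothing in the table or footnote c says when that mark applies. A child seen between doses for an adverse event could be dosed off the four-weekly interval by staff who believe they are following the schedule.

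The first matter at stake is safety. Some events that prompt an unscheduled visit are those for which the protocol stops drug. Footnote c's own example is a patient whose symptoms raise suspicion of PML.

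The second is interpretation. The OLE endpoints in Table 2 include infections, hypersensitivity reactions and anti-drug antibodies under long-term treatment. An unplanned dose close to an adverse event blurs the timing of event relative to dose. Section 6.2 lists and evaluates major protocol deviations, but with two readings of the schedule an off-interval dose cannot be classed consistently as a deviation or as permitted.

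**Working it through.** No sample size, power or error-rate formula applies. The check is a cell count followed by a comparison of passages.

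**1. Do the scheduled columns already carry the whole four-weekly regimen in this part of the table?**
- Four-weekly visits from Week 96 to Week 312, both ends counted: (312 − 96)/4 + 1 = 55.
- Weeks listed in the four scheduled columns: 9 + 36 + 9 + 1 = 55, all marked for dosing.
- The Unscheduled Visit mark is therefore not needed to complete the regimen. It is an additional dosing occasion with no fixed time.

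**2. Is the mark really in the Unscheduled column?**
- The dosing row has five marks and then an empty sixth cell. An empty Early Withdrawal cell is what footnote d requires.
- In the C-reactive protein row of the same part, the fifth cell carries the marker for footnote c (unscheduled visit). The sixth carries the marker for footnote m, which covers a withdrawal that follows an unscheduled visit. The columns are aligned.

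**3. The passages side by side**

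| Place | Dosing at an unscheduled visit |
|---|---|
| Section 3.1 | Every 4 weeks; no other occasion given |
| Section 4.3.2.1 | At treatment visits, according to regimen |
| Appendix 1a, unscheduled column | Not marked |
| Appendix 1c, unscheduled column | Marked |
| Appendix 1c, footnote c | Limits assessments; silent on drug |
| Section 5.1.1.1.1 and Table 4 | Drug withheld for suspected PML; Table 4 also for serious infection |

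The Appendix 1c mark stands alone. No other passage provides for a dose at such a visit, and several point the other way.

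**The case against.** The strongest reply is that a table mark does not override a stated regimen. Section 3.1 fixes the interval, Section 4.3.2.1 ties injections to the regimen, and footnote c says outright that the marked items are not all performed. The withholding rules still apply, and incorrect administration has to be recorded. On this view the mark only lets a due dose be given when an unscheduled visit happens to coincide with it.

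Much of this stands. It rules out reading the mark as an instruction to dose at every unscheduled visit. A reader might also infer that the interval between OLE doses has no lower limit. The documents do not support that, because the four-weekly text and the regimen-based wording set one. The reply does not remove the contradiction, however. Footnote c speaks of assessments and gives no condition for drug, and a coinciding due dose is not among the purposes it lists for the visit.

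A second tempting reading concerns Week 44. In the Weeks 0 to 44 part, the machine-read dosing row shows 11 marks for 12 visits, with Week 44 empty. A reader might infer a skipped dose, an 8-week gap from Week 40 to Week 48, and a much lower Week 48 trough. The documents do not support this. The header over those weeks says every 4 weeks. The machine-read schedules also miscount marks elsewhere: Appendix 1a lacks one ordinary mark in its pharmacokinetic sampling row and has one too many in its concomitant medication row, and the Week 92 label is missing from the next part of Appendix 1c. Any trough calculation would further rest on an adult half-life for a drug whose disposition the protocol calls partly target-mediated.

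**Conclusion.** The inconsistency is real and small. One cell of the Appendix 1c dosing row marks drug at a visit held for an adverse event or possible relapse, with no condition attached. It conflicts with Section 3.1, Appendix 1a and the withholding rules. On its face the table permits an off-interval dose, although the surrounding text makes routine dosing at such visits unlikely.

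The effect on exposure cannot be quantified: the documents give neither the expected number of unscheduled visits nor how often drug would be given at one. The primary pharmacokinetic and pharmacodynamic analyses use the randomized phase and are unaffected. The point deserves correction because this is the dosing schedule for children treated for up to 312 weeks.

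The conclusion assumes that the source page shows the mark where the aligned columns place it. It does not rest on the Week 44 cell, which proves nothing until checked against the source.

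**What to change.** Reconcile the Unscheduled Visit administration cell and footnote c of Appendix 1c with Section 3.1 and with the withholding rules in Section 5.1.1.1.1 and Table 4, so that the schedule gives one consistent dosing instruction. Which rule is right is for the sponsor to settle; none is proposed here. In the same pass, check the Week 44 cell against the source page, with no change implied if the mark is present.

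The cost is one table cell, a sentence in a footnote, or both, in the next amendment. No new data, visits or analyses are needed.
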